1.5 Sample Size

The planned sample size for this trial is 800 randomized and treated subjects. These subjects will be allocated into 4 treatment groups in a 1:1:1:1 ratio. Pair-wise testing of each ALD403 group vs. placebo will be performed. Two hundred subjects per group provides at least 95% power for each change in frequency of migraine days (Weeks 1-12) test individually assuming a treatment effect of at least 1 day and a common standard deviation of 2.7 days or less. Ninety percent power is retained for standard deviations up to 3 days. For the key secondary 75% responder

rates endpoints 95% power is achieved for the pair-wise comparisons assuming rates of 24% for placebo and 42% for ALD403. For the 50% responder rate endpoints 95% power is achieved for the pair-wise comparisons assuming rates of 50% for placebo and 68% for ALD403. For the percentage of subjects with a migraine on the day after dosing endpoint, 95% power is achieved for pair-wise comparisons assuming rates of 15% for placebo and 4% for ALD403.

These sample size calculations have been performed using Pass 2008 and are based upon t-tests and Chi-squared tests that should approximate the ANCOVA and CMH tests, respectively.⁴

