2.2 Clinical Trial Endpoints

The efficacy, safety, pharmacokinetic and immunogenicity of ALD403 will be assessed using the following endpoints. Greater detail concerning these endpoints can be found in Section 2.2.2.

Primary Efficacy Endpoint

• Change in frequency of migraine days (Weeks 1-12)

Key Secondary Efficacy Endpoints

- 75% migraine responder rate (Weeks 1-4)
- 75% migraine responder rate (Weeks 1-12)
- 50% migraine responder rate (Weeks 1-12)
- Percentage of subjects with a migraine on the day after dosing

Other Secondary Efficacy Endpoints

- Change in acute migraine medication days (Weeks 1-12)
- Headaches/Migraines with acute medication usage
- 100% migraine responder rates (Weeks 1-12)
- Short-Form Health Survey (SF-36 v 2.0)
- Health-Related Quality of Life (EQ-5D-5L)
- Allodynia Symptom Checklist-12 (ASC-12)
- Brush (dynamic mechanical) Allodynia
- Migraine responder rates for time periods other than Weeks 1-12
- Change in frequency of migraine days between baseline and time periods other than Weeks 1-12
- Headache responder rates
- Change in the frequency of headache days
- Percent change in headache/migraine days
- Time to first migraine after dosing
- Headache/Migraine hours
- Headache/migraines with severe intensity

Tertiary Endpoints

• Headache episodes/migraine attacks

Exploratory Endpoints

- Headache/Migraine characteristics
- Headaches/Migraines with type of acute medication usage
- Headache episode/Migraine attack average length

Safety Endpoints

- Adverse events (AEs) and serious adverse events (SAEs)
- Changes in clinical laboratory assessments
- Vital Signs
- ECGs
- Suicidal ideation and behavior as measured by the Columbia-Suicide Severity Rating Scale (C-SSRS)

Pharmacokinetic Endpoints

• Free ALD403 plasma concentrations

Immunogenicity Endpoints

- Development of specific anti-ALD403 antibodies
- Characterization of specific anti-ALD403 antibodies for neutralizing activity

2.2.1 eDiary

Subjects will complete a daily headache eDiary from the time of screening to Week 48. The diary is to be completed each trial day whether or not the subject had a headache. These daily entries record if the subject took acute migraine medication on that day.

The eDiary data from the 28 days following screening visit will be used to determine eligibility criteria, and the baseline migraine and headache results.

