The frequency of migraine days is the number of migraine days within four week intervals and the average four week frequency in twelve and twenty-four week intervals. Change from baseline is the difference in frequency between baseline and the counts within these four week intervals. The 12 and 24 week change is the difference in the frequency between baseline and the average of the, 4 week intervals. The percent change is 100 times the ratio of the change and the baseline frequency. Similar measures will be produced based upon headache frequency.

Migraine/ Headache Responder Rate

Three responder rates will be utilized: 50%, 75% and 100%. A responder is a subject who achieves a \geq 50% reduction, \geq 75% reduction, or 100% reduction in migraine days, respectively. These reductions will be evaluated by comparing the baseline frequency of migraine days to the migraine frequency in four week intervals.

Results from the four week intervals will be averaged to produce 12 and 24 week responder endpoints. A responder will be a subject who achieves the specified percent reduction in migraine headache days when response rates for each of the four week intervals are averaged.

Migraine Hours / Headache Hours

Migraine hours are the sum of the duration of migraines within four week intervals, and the average four week duration within 12 and 24 week intervals. Headache hours are similarly defined but include all headaches. Subjects with no migraines/headaches will have a duration of zero.

Migraine Attack / Headache Episode

A migraine attack is defined as 1 continuously recorded migraine. One attack may result in multiple migraine days. Headache episodes are similarly defined.

Migraine / Headache Severity

Headache severity will be collected on a 3 point scale: mild pain, moderate pain, severe pain. The percent of migraines and headaches with severe pain will be summarized. Subjects with no migraines/headaches will be included with a rate of zero.

Acute Medication Usage

The percent of migraines and headaches with acute medication usage as recorded in the eDiary will be summarized. Subjects with no migraines/headaches will be included with a rate of zero.

Acute Migraine Medication Usage

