2.3 Trial Day

Trial endpoints will be reported within analysis windows or analysis intervals based upon the actual date of the assessment. Assignment of results to these time points is based upon the trial day. Trial day is defined as:

Trial day = date of assessment - date of treatment

Analysis Windows used to report non-diary endpoints are outlined in Table 2.

Table 2: Analysis Windows

Visit	Range	Target Day	If more than one which one is used
			for analyses
Screening	< Day 0		First value
Day 0	Day 0 to Day 7	Day 0	Day 0
Week 4	Day 8 to Day 42	Day 28	Closest to Target Day
Week 8	Day 43 to Day 70	Day 56	Closest to Target Day
Week 12	Day 71 to Day 98	Day 84	Closest to Target Day
Week 16	Day 99 to Day 126	Day 112	Closest to Target Day
Week 20	Day 127 to Day 154	Day 140	Closest to Target Day
Week 24	Day 155 to Day 182	Day 168	Closest to Target Day
Week 28	Day 183 to Day 210	Day 196	Closest to Target Day
Week 36	Day 211 to Day 273	Day 252	Closest to Target Day
Week 48	Day 274 to Day 357	Day 336	Closest to Target Day
Week 56	> Day 357	Day 392	Closest to Target Day

Note: If two observations exist with same distance to target day, use first observation.

For the eDiary data used to produce the migraine and headache endpoints the intervals specified in Table 3 will be used to collapse the daily data into 4, 12, and 24 week intervals. For these data baseline is defined as the 28 days starting on the day of the first diary entry.

Table 3: eDiary Headache/Migraine Endpoint Analysis Intervals

Diary			
Weeks	Trial Time	Comments	Endpoints
Baseline	The 28 days starting from the first eDiary entry		All eDiary related endpoints
1-4	Days: 0-27	Day 0 = First day of treatment	All eDiary related endpoints
5-8	Days: 28-55		All eDiary related endpoints
9-12	Days: 56-83		All eDiary related endpoints
1-12	Weeks 1-4, 5-8 and 9-12	Average of the 4 week intervals after imputation methods are applied	All Primary and Secondary eDiary related endpoints
13-16	Days: 84-111		All eDiary related endpoints
17-20	Days: 112-139		All eDiary related endpoints
21-24	Days: 140-167		All eDiary related endpoints
13-24	Weeks 13-16, 17-20 and 21-24	Average of the 4 week intervals after imputation methods are applied	All Primary and Secondary eDiary related endpoints
1-24	Weeks 1-4, 5-8, 9-12, 13-16, 17-20 and 21-24	Average of the 4 week intervals after imputation methods are applied	All Primary and Secondary eDiary related endpoints
25-28	Days: 168-195	1 11	All eDiary related endpoints

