3.4 Analysis of Efficacy Endpoints

3.4.1 Headache/Migraine Days and Acute Migraine Medication Days

Summary tables for the number of migraine/headache days, change from baseline and the percent change by 4, 12 and 24 week intervals and treatment group will be produced. Similar tables will be produced for acute migraine medication days and the change from baseline acute migraine medication days. The treatment difference and associated confidence interval will also be provided. These confidence intervals will be based on normal approximation. Stratification will not be used for these intervals.

Additionally, the SAS procedure, Proc Mixed using the ANCOVA model controlling for the effects of baseline migraine days outlined in Section 2.5, will be used to calculate the estimated treatment difference from placebo, the change from baseline and the associated confidence intervals for Weeks 1-12. The ANCOVA model will also be used to test for a treatment difference in the primary endpoint change from baseline in migraine days for Weeks 1-12 and for the change from baseline days of acute migraine medication use for Weeks 1-12. Significant p-values based on the formal decision rule criteria outlined in Section 2.7.5 will be clearly noted.

Plots of the migraine days and change from baseline and for days of acute migraine medication use and change from baseline will be produced. These plots will use the four week intervals as

the X-axis. A separate set of graphs that provide histograms of the Week 1 to 12 results for these three parameters will also be produced.

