The change from baseline in migraine days for the six, 4 week intervals from Weeks 1 to 24 will also be analyzed using repeated measures. The model will include treatment group, timepoint (Weeks 1-4, 5-8 9-12, 13-16, 17-20, 21-24), and baseline migraine days as fixed factors. Estimated treatment difference, for each timepoint, and associated confidence interval will be estimated using SAS procedure, Proc Mixed. The unstructured (UN) covariance structure will be specified. If the model fails to converge, an alternative covariance structure will be specified. The timepoint variable will be categorical and baseline migraine days will be continuous. The repeated measures analysis will be repeated for weeks 1-12 using the same subjects and a subset where only subjects/four week intervals where the eDiary was completed a minimum of 21 days and applying Missing Data Rule 1 described in Section 2.2.2. Only the overall week 1-12 estimated treatment difference, associated confidence interval and p-value will be reported for this analysis.

The change from baseline in migraine days for Weeks 1-12 will be summarized within the subgroups outlined in Section 2.7.1 forest plot of the treatment difference and associated confidence interval will also be presented.

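### The Weeks 1-24 repeated-measures model names no treatment-by-timepoint term, so as written it cannot give the separate interval differences that the SAP promises

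*SAP*

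**What the plan says.** SAP 3.4.1 says that change from baseline in migraine days "for the six, 4 week intervals from Weeks 1 to 24 will also be analyzed using repeated measures". The specification follows: "The model will include treatment group, timepoint (Weeks 1-4, 5-8 9-12, 13-16, 17-20, 21-24), and baseline migraine days as fixed factors". Timepoint is categorical, baseline is continuous, and the covariance is unstructured. The promised output is: "Estimated treatment difference, for each timepoint, and associated confidence interval will be estimated using SAS procedure, Proc Mixed".

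The same paragraph repeats the model for Weeks 1-12 and reports only an overall difference.

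Three other places bear on this:

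- SAP 2.2 lists among the other secondary endpoints: "Change in frequency of migraine days between baseline and time periods other than Weeks 1-12".
- Earlier in SAP 3.4.1, summary tables by 4-, 12- and 24-week interval are specified, and for these "The treatment difference and associated confidence interval will also be provided". Those confidence intervals use a normal approximation without stratification.
- The ANCOVA with baseline as covariate (SAP 2.5 and 3.4.1) is specified for Weeks 1-12 only.

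No treatment-by-timepoint term is named in SAP 2.5, in SAP 3.4.1 or elsewhere in the SAP. The protocol does not describe this model.

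**The concern.** The stated model and the stated output do not match. A model with additive treatment and time effects assumes that each dose has the same effect in all six intervals. Asked for a difference at each timepoint, it returns one number six times.

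This model is the only planned source of covariate-adjusted differences by 4-week interval. Run literally, the report would set six unadjusted differences, which can vary, beside six identical adjusted ones, with no stated reason. A reader could take the identical values as evidence of a stable effect when the model imposed them. Proc Mixed fits the additive model without any error message, so the mismatch could reach the tables unnoticed.

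**Working it through.** The SAP gives no figure for this model, so there is none to reproduce. The check has a structural part and an illustration of size.

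**Structure.** Inputs: four arms (SAP 1.5) and six intervals (SAP 3.4.1). Under the listed model the mean for dose *g* in interval *t* is

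μ(g,t) = α + τ(g) + π(t) + β × baseline.

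The difference from placebo in interval *t* is [τ(g) + π(t)] − [τ(0) + π(t)] = τ(g) − τ(0). The time terms cancel, so *t* drops out.

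| Model | Mean parameters, without the baseline slope | Distinct dose-placebo differences |
|---|---|---|
| As listed | 1 + 3 + 5 = 9 | 3 |
| With treatment-by-timepoint | 9 + 3 × 5 = 24 | 3 × 6 = 18 |

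The promised output needs 18. The covariance structure sets the weights and standard errors but adds no mean parameters.

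One simulated data set shows the effect (200 per arm, interval SD 2.7, correlation 0.6, true 300 mg differences −1.4, −1.2, −0.8, −1.3, −1.0, −0.6). The listed model gave −1.066 (SE 0.215) in all six intervals. With the interaction it gave −1.31, −1.05, −0.78, −1.37, −1.05 and −0.61 (SE 0.26 to 0.28).

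**Size.** From SAP 1.5: 200 per arm and "assuming a treatment effect of at least 1 day and a common standard deviation of 2.7 days or less". Assumed, because the documents do not give them: complete data, equal SDs, equal correlation *r* of 0.4, 0.6 or 0.8 between intervals, and the size of any departure from a constant effect. The SD of 2.7 is taken as the residual SD of the Weeks 1-12 average.

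- Interval SD: s = 2.7 / √[(1 + 2r)/3]
- SE of an interval-specific difference: s√(2/200) = 0.1s
- SE of the common difference: 0.1s√[(1 + 5r)/6]

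| r | s | Interval SE | Common SE | Ratio |
|---|---|---|---|---|
| 0.4 | 3.49 | 0.349 | 0.246 | 1.41 |
| 0.6 | 3.15 | 0.315 | 0.257 | 1.22 |
| 0.8 | 2.90 | 0.290 | 0.265 | 1.10 |

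If the true effect in an interval departs by *b* from the average, the common 95% interval covers it with probability Φ(1.96 − b/SE) − Φ(−1.96 − b/SE). For r = 0.4 and b = 0.30: 0.30/0.246 = 1.22, and coverage is 0.770.

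Let the first and third intervals of each 12-week dosing cycle depart by ∓b and the middle ones by zero:

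| b (days) | Coverage, 4 departing intervals | Coverage, 2 middle intervals | Mean of six |
|---|---|---|---|
| 0 | 95% | 95% | 95% |
| 0.15 | 91% | 95% | 92% |
| 0.30 | 77-80% | 95% | 83-85% |
| 0.50 | 47-53% | 95% | 63-67% |

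A steady drift over 24 weeks with the same end departures gives six-interval means of 93%, 87-88% and 73-75%. With autoregressive correlation of 0.4 to 0.8, the cyclic pattern gives 91-92%, 78-82% and 53-61%.

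A simulation with four arms, a baseline covariate and an estimated unstructured covariance (300 trials per scenario) agreed. At b = 0.30 the listed model covered 77-81% in the departing intervals. With the interaction added, coverage was 92-98% in every interval in all scenarios.

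**Overall Weeks 1-12 difference.** The primary endpoint averages three intervals equally: "The 12 and 24 week change is the difference in the frequency between baseline and the average of the, 4 week intervals". The additive model weights by the inverse covariance instead. With equal SDs and equal correlation the two agree. With assumed SDs of 2.85, 3.15 and 3.46 and r = 0.6, the weights are 0.55, 0.31 and 0.14. The overall figure then moves by −0.06, −0.12 or −0.20 day for first- and third-interval departures of 0.15, 0.30 or 0.50. The sign reverses if the SDs fall over time.

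**The case against.** The strongest reply is that the list is shorthand. The text names terms that the model will include and does not say that there are no others. With categorical time, unstructured covariance and a difference requested at each timepoint, many statisticians would add the interaction without asking. That may be what was meant. But the list runs as written, and the overall Weeks 1-12 difference in the same paragraph is something an additive model supplies directly. The wording therefore allows both readings.

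Second, the secondary endpoint is already served by the unadjusted interval differences in SAP 3.4.1, which are valid in a randomized trial. They are on change from baseline, under randomization stratified by migraine days. This stands. What is at risk is only the regression-adjusted version, in a supportive analysis.

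Third, the coverage losses depend on departures that no document reports. Protocol 5.3.3 describes sustained efficacy after a single 1000 mg dose, and 12-week suppression of a skin blood flow marker at 100 mg and above. This does not point to the cyclic pattern assumed here. Nor does it establish a constant effect on migraine days, least of all at 30 mg. The departures are illustrations, and 0.50 day, half of the assumed 1-day effect, is an upper bound.

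Fourth, a gap between an unadjusted and a pooled difference would not by itself show the pooled value wrong. Under a constant effect the gap has SD √(interval SE² − common SE²), which is 0.25, 0.18 or 0.12 day for the three correlations.

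**Conclusion.** The point holds and is minor. As written, the model yields three differences where eighteen are promised; this follows from the listed terms and needs no assumption. Whether harm follows depends on the true time course. A constant effect gives valid pooling, no bias and 95% coverage. With departures of 0.15 to 0.50 day in four of six intervals, coverage there falls to between 91% and 47% under the equal-correlation assumptions. Nothing in the primary ANCOVA, the key secondary tests, the multiplicity procedure in SAP 2.7.5 or the sample size is affected.

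**What to change.** In SAP 3.4.1, add treatment-by-timepoint to the fixed effects and take the six interval differences and confidence intervals from its least-squares means.

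As a clarification rather than a correction, add a sentence that the overall Weeks 1-12 difference from this model is the equally weighted mean of the Weeks 1-4, 5-8 and 9-12 differences. That matches the rule for the 12-week endpoint in SAP 2.3, Table 3: "Average of the 4 week intervals after imputation methods are applied".

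The change costs one model term and one sentence, with no cost in patients, data or alpha. The interval-specific confidence intervals will be 1.10 to 1.41 times as wide as the pooled one under equal correlation of 0.4 to 0.8, and 1.25 to 1.77 times under autoregressive correlation of the same range. That width is the price of estimates that are specific to each interval. In the Weeks 1-12 example with unequal SDs, equal weighting raises the SE only from 0.264 to 0.270.

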3.4.2 Responder Rates

The responder rates will be determined as outlined in the missing data Section 2.7.2 and the endpoint definition in Section 2.2.2. The number of subjects who are responders and the rate (full analysis population as the denominator) will be summarized for each treatment group and at each 4, 12 and 24-week interval. The difference in rates and associated confidence interval will also be produced. These confidence intervals will be calculated based upon the normal approximation for two independent proportions. Stratification will not be used for these intervals. The SAS procedure, Proc Freq, will be used to calculate these confidence intervals. Any interval for which the normality assumption is questionable (i.e. np <5 or nq <5) will be flagged.

Plots of the percent of responders across time, for each response level, will be produced. These plots will use the four-week responder rates.

A p-value for the difference in rates for the key secondary endpoints will be based upon the CMH test outlined in Section 2.5. Significant p-values based on the formal decision rule criteria outlined in Section 2.7.5 will be clearly noted in the footnotes.

Should the as randomized and 'true' values for the stratification factors differ the as randomized values will be used within these CMH tests. The SAS procedure, Proc Freq, will be used to calculate this p-value.

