1.3 Method of Assigning Subjects to Treatment Groups

Randomization will occur 29 to 35 days after the screening visit when the eligibility assessments are completed and eligibility verified. Sites will complete the randomization using an Interactive Web Response System (IWRS) and the randomization assignment will be obtained by the clinical trial site's unblinded pharmacist or Investigational Product consignee. Subjects will be randomized in equal ratios to one of the four 4 treatment groups (30 mg, 100 mg, or 300 mg of ALD403 or Placebo). Stratified permuted block randomization will be used. Stratification will be by migraine days during the screening period (≤9 days vs. >9 days).

Randomized subjects who terminate their clinical trial participation for any reason, regardless of whether Investigational Product was taken or not, will retain their randomization assignment and subject number.

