2.5 Statistical Assessment of the Trial Objectives

Hypothesis testing will be performed for the primary endpoint: change from baseline in migraine days from Weeks 1-12. This endpoint will be calculated as outlined in Section 2.2.2 and will utilize the missing data rules provided in Section 2.7.2. The hypotheses tested are

$$H_o: \Delta_{plb} = \Delta_{403} H_a: \Delta_{plb} \neq \Delta_{403}$$

where Δ_{403} is the change in migraine days for subjects in the ALD403 treatment arm and Δ_{plb} is similarly defined for the placebo subjects. The change from baseline is expected to be negative as migraines are being reduced. While the test outlined above is two sided, as is the alpha level used for this study (i.e. 5%), clinically relevant results require a larger reduction of migraines on the ALD403 arms.

An ANCOVA model will be used to test for a difference between treatment arms. This model will include the change from baseline measure as the response variable. Treatment and the stratification variable: baseline migraine days (continuous covariate) will be the independent variables.

In addition, model based estimates including confidence intervals for the treatment differences will be used to summarize the results for the primary endpoint.

A sensitivity analysis of the change from baseline in migraine days will be performed using the sensitivity missing data rule provided in Section 2.7.2.

Secondary Efficacy Analyses

Summary statistics including confidence interval for the treatment differences will be used to summarize the results for the secondary endpoints. Testing will be performed for the key secondary endpoints and for the change in acute migraine medication days endpoint. For the key secondary endpoints (responder rates and percentage of subjects with a migraine on the day after dosing) this testing will utilize a CMH/extended CMH test. The tests will be stratified by the randomization stratification factor. The change in acute migraine medication day endpoints will be tested using an ANCOVA model similar to the one used for the primary endpoints: change from baseline measure as the response, treatment and baseline acute migraine medication days as independent variables. The time to first migraine analysis will be descriptively summarized based upon Kaplan-Meier methods.

Exploratory Analyses

Exploratory endpoints will be summarized with descriptive statistics by treatment group.

20

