2.7.5 Multiple Comparisons/Multiplicity

A serial procedure will be used to account for multiplicity of dose level for the primary endpoint and the secondary endpoints. This procedure will start with the 300 mg vs placebo comparison for the primary endpoint. If this is significant, testing will continue to a subset of the key secondary endpoints for 300 mg (first the Weeks 1-4 75% responder endpoint, then the Weeks 1-12 75% responder endpoint, and then the Weeks 1-12 50% responder endpoint). The procedure will then move on to the primary endpoint for the 100 mg group and subsequently to the same subset of key secondary endpoints as tested for the 300 mg dose. The procedure will then move on to the remaining key secondary endpoint for 300 mg and 100 mg (i.e., percentage of subjects with a migraine on the day after dosing). Only if all of these secondary endpoints reach statistical significance will the 30 mg group be tested.

Statistical testing will be conducted at the 5% alpha level.

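### Three key secondary responder rates are tested with a stratified CMH test, but their differences get only an unstratified interval: a minor reporting gap

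*SAP*

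**What the plan says.** Randomization is stratified by migraine days in the screening period, at most 9 against more than 9 (SAP 1.3; Protocol 8.3.2). For the key secondary endpoints, SAP 2.5 plans a CMH or extended CMH test and adds: "The tests will be stratified by the randomization stratification factor". SAP 3.4.2 takes the responder p-values from that test and says that, where the randomized and true strata differ, "the as randomized values will be used within these CMH tests".

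For the size of the effect, SAP 3.4.2 plans the difference in rates with one interval: "These confidence intervals will be calculated based upon the normal approximation for two independent proportions. Stratification will not be used for these intervals". SAP 2.5 and Protocol 13.4.2 otherwise offer only summary statistics with a confidence interval for secondary endpoints. Neither document plans a stratum-weighted difference, a common odds ratio or a model-based estimate for responder rates.

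The primary endpoint is handled differently. SAP 3.4.1 also gives migraine days an unstratified interval, but it then adds ANCOVA estimates for Weeks 1-12, and SAP 2.5 says that "model based estimates including confidence intervals for the treatment differences will be used to summarize the results for the primary endpoint".

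The fourth key secondary endpoint (migraine on the day after dosing, SAP 3.4.3.1) uses an extended CMH test and names no interval method. It is outside this point.

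**The concern.** The three responder endpoints sit in the serial testing order (SAP 2.7.5) for 300 mg and 100 mg, and for 30 mg if testing gets that far. Each will be reported with a p-value from a stratified analysis beside an interval from an unstratified one. If response differs between strata, the crude interval carries the between-stratum variation that the test removes, so it is slightly wider than it needs to be. In principle it could include zero beside a significant p-value. At stake is how the effect is reported. The claim of significance rests on the CMH test alone.

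**Working it through.** **Inputs from the documents.** 200 per arm (SAP 1.5: "Two hundred subjects per group provides at least 95% power"); 5% alpha (SAP 2.7.5), two-sided (SAP 2.5); planned rates of 24% against 42% (75% response) and 50% against 68% (50% response).

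**The plan's own figure.** SAP 1.5 states 95% power for both pairs of rates, from chi-squared tests. With the pooled test, power = Φ{[d − 1.96·√(2p̄(1−p̄)/n)] / √([p0(1−p0)+p1(1−p1)]/n)}:
- 24 vs 42: (0.18 − 1.96×0.04702)/0.04615 = 1.90, power 97.1%
- 50 vs 68: (0.18 − 1.96×0.04918)/0.04835 = 1.73, power 95.8%

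With continuity correction the figures are 96.4% and 94.8%. The stated 95% is reproduced.

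**Assumptions.** The documents give neither the stratum shares nor the responder rates by stratum. I take a gap g of 0 to 20 points between strata, equal in both arms, and shares w of 50/50 to 70/30, with the overall rates held at the planned values.

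**Half-widths.**
- Crude: 1.96·√{[p0(1−p0)+p1(1−p1)]/200}. For 24 vs 42 this is 1.96·√(0.4260/200) = 9.05 points. For 50 vs 68 it is 1.96·√(0.4676/200) = 9.48 points.
- Stratified: the same, with 2w(1−w)g² taken off the numerator. For 24 vs 42, w = 0.5, g = 0.20: 0.4260 − 2×0.25×0.04 = 0.4060, so 1.96·√(0.4060/200) = 8.83 points.

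| Rates | Crude | g = 0 | g = 5 | g = 10 | g = 20 |
|---|---|---|---|---|---|
| 24 vs 42 | 9.05 | 9.05 | 9.03 | 8.99-9.00 | 8.83-8.87 |
| 50 vs 68 | 9.48 | 9.48 | 9.46-9.47 | 9.43 | 9.27-9.31 |

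The largest reduction is 9.046 − 8.831 = 0.215 points, or 0.215/9.046 = 2.4%.

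**Coverage** (simulation, 400,000 trials per scenario; stratified = Mantel-Haenszel risk difference with Sato variance). Crude: 94.9-95.2% at a 10-point gap and 95.3-95.5% at 20. Stratified: 94.8-95.0%.

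**Point estimate.** With arms at most one subject apart per stratum (assumed, as no block size is given), the two estimates differ with an SD of 0.03 points (gap 10) or 0.06 points (gap 20). With a three-subject imbalance the mean shift is 0.05-0.3 points and the largest 0.7.

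**Disagreement with the CMH verdict at the 5% level**, % of trials, near-balanced strata, range over the shares:

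| Rates | Gap 10: crude | Gap 10: stratified | Gap 20: crude | Gap 20: stratified |
|---|---|---|---|---|
| 24 vs 42 | 0.045-0.051 | 0.062-0.069 | 0.177-0.242 | 0.072-0.080 |
| 50 vs 68 | 0.068-0.095 | 0.134-0.160 | 0.388-0.451 | 0.122-0.138 |
| 24 vs 34 | 0.304-0.346 | 0.443-0.467 | 1.082-1.320 | 0.382-0.441 |
| 50 vs 60 | 0.042-0.050 | 0.105-0.127 | 0.860-1.231 | 0.612-0.759 |

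The last two rows assume a weaker 10-point effect. At a zero gap the two intervals disagree with CMH about equally often. At 5 points the stratified one disagrees slightly more often in all eight scenarios run (four rate pairs, two shares). The balance assumption matters: with three subjects out of balance in a stratum (35% share, 24 vs 34, gap 10), the crude interval disagreed in 1.43% of trials and a stratum-weighted Wald interval in 0.63%.

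**The variance must be named.** For 50 vs 60, gap 20, shares 50/50, disagreement is 1.20% crude, 0.76% with the Sato variance and 1.12% with the stratum-weighted Wald variance.

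**The case against.** The strongest reply is that nothing is broken. The SAP says outright that these intervals are unstratified. Under 1:1 randomization the crude difference is a valid estimate with correct coverage, and the deciding test already uses the strata. Response is a percent reduction from the subject's own baseline (SAP 2.2.2), so the gap between strata may well be small, and at zero gap there is no gain in width. SAP 3.1 prints percentages to one decimal, so a change of 0.05 points at a 10-point gap would mostly not show. The primary endpoint is also only a loose parallel, because its ANCOVA adjusts for continuous baseline migraine days and not for the two strata.

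All of this stands, and it fixes the size of the point. It does not remove it: three formally tested endpoints have no estimate built on the same stratification as their test, and supplying one needs nothing that the analysis does not already hold.

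A reader might infer more than the documents support:
- That SAP 2.5 and 3.4.2 contradict each other. They do not; one describes the test and the other the interval.
- That the crude interval is wrong or undercovers. Its coverage is at or slightly above 95%.
- That type I error, power or the testing order is affected. These rest on the CMH p-values.
- That a stratified interval would bring interval and p-value into line. With near-balanced strata it agrees no better at gaps of 10 points or less, and better only at about 20.

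**Conclusion.** The point holds as a minor reporting improvement. The three key secondary responder differences have an interval that does not use the stratification of their test. Over the assumed range, a stratified interval is never wider on average. It is equal at no gap, about 0.5% narrower at 10 points and about 2% (at most 2.4%) narrower at 20. The case for it is an estimate that matches the test, plus that small gain in precision.

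The size rests on assumed stratum shares and gaps, 200 per arm, the planned rates and near-balanced strata. The absence of a planned stratified estimate rests on the text alone.

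**What to change.** In SAP 3.4.2, for the 75% (Weeks 1-4), 75% (Weeks 1-12) and 50% (Weeks 1-12) migraine responder rates, add a sentence: each ALD403 dose will also be compared with placebo by the Mantel-Haenszel common risk difference with a 95% confidence interval using the Sato variance, on the as-randomized strata of the CMH test. Keep the crude rates, differences and intervals as descriptive columns.

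The cost is that sentence and one extra column in the tables of three endpoints. SAP 3.4.2 already names the SAS frequency procedure for both the interval and the test, and the strata are already in the analysis. No new data are needed, and neither the tests nor the decision rule change. The sentence belongs in the SAP before the Week 24 unblinding (SAP 1.4), so that the choice of estimate is not made after the results are seen.
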